5.1.2. Exclusion Criteria

Potential study patients may not be included in the study if any of the following apply:

- [13] Have received treatment with a drug that has not received regulatory approval for any indication within 14 or 21 days of the initial dose of study drug for a nonmyelosuppressive or myelosuppressive agent, respectively.
- [14] Have a personal history of any of the following conditions: presyncope or syncope of either unexplained or cardiovascular etiology, ventricular arrhythmia (including but not limited to ventricular tachycardia and ventricular fibrillation), sudden cardiac death, or sudden cardiac arrest.
- [15] Exclusion Criterion [15] has been deleted.

- [16] Have serious preexisting medical conditions that, in the judgment of the investigator, would preclude participation in this study (for example, history of major surgical resection involving the stomach or small bowel).
- [17] For Dose Escalation (Part A): Have CNS malignancy or metastasis. Screening of asymptomatic patients without history of CNS metastases is not required for enrollment.
For Dose Confirmation (Parts B, D, E, F, and G): Have CNS metastasis that is radiographically or clinically unstable less than 14 days prior to receiving study drug, regardless of whether they are receiving corticosteroids.
For Dose Confirmation (Part C): Have GBM that is radiographically or clinically unstable less than 14 days prior to receiving study drug, regardless of whether they are receiving corticosteroids.
- [18] Have an acute leukemia.
- [19] Have received an autologous or allogeneic stem-cell transplant within 75 days of the initial dose of study drug. In addition, recipients of an allogenic stem-cell transplant must have discontinued immunosuppressive therapy at least 11 days before study drug administration with no more than Grade 1 acute graft-versus-host disease (refer to [Attachment 7](#) for grading and staging of graft-versus host disease) on Day-3.
- [20] Females who are pregnant or lactating.
- [21] Have active bacterial, fungal, and/or known viral infection (for example, human immunodeficiency virus [HIV] antibodies, hepatitis B surface antigen [HBSAg], or hepatitis C antibodies). Screening is not required for enrollment.

5.2. Summary of Study Design

This study is a multicenter, nonrandomized, open-label, dose-escalation Phase 1 trial of LY2835219 in approximately 300 patients with advanced cancer. During dose escalation (Part A), 33 patients were treated across 2 schedules. For the once daily schedule, patients received LY2835219 orally every 24 hours. For the twice daily schedule, patients received LY2835219 orally every 12 hours for Days 1 through 28 of a 28-day cycle (refer to [Figure JPBA.5.1](#)), with modifications during Cycle 1 to enable PK sampling following a single dose and repeated doses. During dose escalation, cohorts of at least 3 patients were enrolled at each of the planned dose levels.

[figure not shown]
During dose escalation (Part A), 33 patients were treated across 2 schedules. For the once daily schedule, patients were treated at 50, 100, 150, and 225 mg every 24 hours (Q24H). For the twice daily schedule, patients were treated at 75, 100, 150, 200, and 275 mg every 12 hours (Q12H). An MTD for the once daily schedule was not reached, whereas the MTD for the twice daily schedule was tentatively established (pending dose confirmation) at 200 mg Q12H. As depicted in [Figure JPBA.5.1](#), the study design consists of a *dose escalation phase (Part A)* and *6 tumor-specific expansion phases (Parts B, C, D, E, F, and G)*. The dose escalation phase

(Part A), described in Section 6.2.2, was guided by safety assessments from Days 1 through 28 of Cycle 1 for all patients in the cohort and also by the emerging PK data. Dose escalation occurred until the MTD (defined in Section 6.2.2.1) was determined for at least 1 schedule.

After the last patient enrolled in the dose escalation phase (Part A) completes Cycle 1, then the 6 tumor-specific expansion phases (Parts B, C, D, E, F, and G) may begin. In each tumor-specific expansion phase, at least 15 and up to 45-60 patients will be treated on the twice daily schedule at a dose no greater than the MTD (200 mg every 12 hours) with administration of LY2835219 on Days 1 through 28 of a 28-day cycle, with modifications during Cycle 1 to enable PK sampling following a single dose and repeated doses. Patients enrolled in Part G should receive fulvestrant according to the study schedule.

All patients in the study receive 2 cycles of LY2835219 unless one or more of the criteria for discontinuation (refer to Section 5.3.1) are fulfilled; the follow-up period for poststudy evaluation is 30 ± 7 days from the date of the last dose of study drug received. A patient may receive more than 2 cycles of treatment only if 1) none of the criteria for discontinuation have been fulfilled, and 2) the investigator, in consultation with the Lilly clinical research physician (CRP), determines that the patient is experiencing clinical benefit from treatment.

Refer to [Attachment 1](#) for the detailed study schedule.

Abbreviations: HR+ = hormone receptor positive; Q12H = every 12 hours;
Q24H = every 24 hours.

Figure JPBA.5.1. Study design for I3Y-MC-JPBA.

5.3. Discontinuations

5.3.1. Discontinuation of Patients

The criteria for enrollment must be followed explicitly. If a patient who does not meet enrollment criteria is unintentionally enrolled, Lilly or its designee must be contacted. In these rare cases, the investigator must obtain documented approval from Lilly to allow the patient to continue in the study.

In addition, patients will be discontinued from the study in the following circumstances:

- The investigator or attending physician decides the patient should be withdrawn. If this decision is made because of a serious adverse event or a clinically significant laboratory value, then appropriate supportive measures are to be taken. Lilly or its designee is to be alerted immediately. (Refer to Section 7.1).
- The patient requests to be withdrawn from the study.
- The patient, for any reason, requires treatment with another therapeutic agent that has proven efficacious in the treatment of the study indication. In this case, discontinuation from the study occurs prior to introduction of the new agent.
- The investigator or Lilly, for any ethical, medical, or scientific reason, while considering the rights, safety, and well-being of the patient(s), stops the study or stops the patient's participation in the study.
- The patient experiences unacceptable toxicity, including but not limited to the following circumstance (refer to Section 6.2.4.2):
 - The patient does not meet the criteria for recovery from toxicity within 14 days of the last day of the previous cycle.
 - The patient is noncompliant with study procedures and/or treatment.(refer to Section 6.6).
 - The patient has evidence of progressive disease.

Patients who discontinue the study drug and/or study early will have end-of-study and follow-up procedures performed as shown in the Study Schedule ([Attachment 1](#)).

For dose escalation (Part A), any patient who is discontinued from the study before receiving at least 75% of planned doses of LY2835219 in Cycle 1 will be deemed nonevaluable for assessment of that dose level and may be replaced unless they experience a DLT before withdrawal. Nonevaluable patients may be replaced to ensure that no fewer than 3 patients receive at least 75% of planned doses of LY2835219 in Cycle 1 at each dose level, unless enrollment to that cohort has stopped because more than 1 patient at that dose level has experienced a DLT. Patients who complete Cycle 1 of therapy but are not evaluable for PK may be replaced upon consultation with the investigator(s) and the Lilly CRP to ensure adequate PK

data collection, unless enrollment to that cohort has stopped because more than 1 patient at that dose level has experienced a DLT.

For Part G, any patient who is discontinued from the study for a reason other than progressive disease and before receiving a post-treatment radiological tumor assessment will be deemed nonevaluable for assessment of response. Additional patients may be enrolled to replace nonevaluable patients.

5.3.2. Discontinuation of Study Sites

Study site participation may be discontinued if Lilly, the investigator, the institutional review board (IRB)/ethical review board (ERB) or the regulatory authority deems it necessary for any scientific, medical, or ethical reason.

5.3.3. Discontinuation of the Study

The study will be discontinued if Lilly, while considering the rights, safety, and well-being of the patient(s), deems it necessary for any scientific, medical, or ethical reason.

6. Treatment

6.1. Materials and Supplies

LY2835219 will be supplied by the sponsor for oral administration. LY2835219 should be stored at room temperature according to the label, and not opened, crushed, or dissolved. Investigators should instruct patients to store LY2835219 in the original package and in a location inaccessible to children. Clinical study materials will be labeled according to US regulatory requirements.

For Part G, patients with HR+ breast cancer should receive fulvestrant as specified in the label. Fulvestrant (50 mg/mL) is available commercially, should be stored and administered according to the label, and will not be supplied.

6.2. Treatments Administered

The investigator or his/her designee is responsible for:

- explaining the correct use of the investigational agent and planned duration of each individual's treatment to the patient and, if appropriate, to the patient's designated legal representative,
- verifying that instructions are followed properly,
- maintaining accurate records of study drug dispensation, destruction, and collection, and
- returning or destroying all unused medication to Lilly or its designee at the end of the study.

Patients will be instructed to contact the investigator as soon as possible if they have a complaint or problem with the study drug so that the situation can be assessed.

6.2.1. Dosing Schedule

For the once daily schedule, patients will continue to receive LY2835219 orally every 24 hours (± 3 hours) for Days 1 through 28 of a 28-day cycle. For the twice daily schedule, patients will receive LY2835219 orally every 12 hours (± 3 hours) for Days 1 through 28 of a 28-day cycle. For both schedules, there are modifications during Cycle 1 to enable PK sampling following a single dose and repeated doses.

During Cycle 1 on the twice daily schedule, the initial dose of study drug will be taken on Day -3 to enable PK sampling over 72 hours following a single dose; the remaining 55 doses will be taken every 12 hours on Days 1 to 28, with PK sampling on Day 1 and Day 15 and over 24 hours following the single dose taken on Day 28. For Cycle 1, patients should be specifically instructed not to take a second dose of study drug on Day 28; if such a dose is inadvertently taken on Day 28, it constitutes a protocol violation. Patients should not consume food beginning 1 hour before and ending 1 hour after taking study drug.

During Cycle 2 and beyond on the twice daily schedule, study drug is taken orally every 12 hours on Days 1 through 28 of a 28-day cycle.

During all cycles, study drug should be taken at approximately the same time(s) each day. If a patient misses or vomits a dose, that dose should be omitted. Patients must record the time and amount of each dose taken (or alternatively, the time and amount of the dose missed or vomited) in a daily diary.

For Part G, patients should receive fulvestrant according to the study schedule. For patients already receiving fulvestrant at time of study entry, the fulvestrant dose on Cycle 1 Day 1 should correspond approximately to the expected date for its monthly administration and fulvestrant should not be administered on Cycle 1 Day 15.

For Part G, fulvestrant 500 mg should be administered intramuscularly into the buttocks slowly (1 to 2 minutes per injection) as two 250-mg injections, one in each buttock; however, for patients with moderate hepatic impairment (defined as Child-Pugh Class B), fulvestrant 250 mg should be administered intramuscularly into the buttock slowly (1 to 2 minutes) as one 250-mg injection.

Patients will receive 2 cycles of LY2835219 unless one or more of the criteria for discontinuation (refer to Section 5.3.1) are fulfilled; the follow-up period for poststudy evaluation will be 30 ± 7 days from the date of the last dose of study drug received. A patient may receive more than 2 cycles of treatment only if 1) none of the criteria for discontinuation have been fulfilled, and 2) the investigator, in consultation with the Lilly CRP, determines that the patient is experiencing clinical benefit from treatment.

For Cycle 2 and beyond, a delay of ≤ 7 days in the start of a cycle (Day 1) for justifiable reasons (for example, inclement weather, holidays, or weekends) other than toxicity will be permitted and does not constitute a protocol violation.

For Cycle 2 and beyond, a delay of ≤ 14 days in the start of a cycle (Day 1) to allow for recovery from toxicity will be permitted and does not constitute a protocol violation (refer to Section 6.2.4.2).

6.2.2. Dose-Escalation Phase

The dose was escalated following assessment of toxicity using the standard scoring system, Common Terminology Criteria for Adverse Events (CTCAE CCI [REDACTED] established by the National Cancer Institute (NCI). Any AEs possibly related to LY2835219 were considered as toxicities.

For the dose-escalation phase, Table JPBA.6.1 summarizes the dose levels completed for the once daily schedule (50 to 225 mg every 24 hours) and the proposed dose levels for the twice daily schedule (75 to 450 mg every 12 hours). Three patients were planned for treatment at each dose level; however, the exact number of patients treated at a specific dose level depended, as discussed below, on the number of patients within the cohort who experienced a DLT. If a patient in a given cohort experienced a DLT during Cycle 1, then subsequent patients were enrolled sequentially.

In all cohorts (including the first cohort), every patient was assessed for toxicity (based on CTCAE CCI [REDACTED] grading) on Days 15 and 29 of Cycle 1. Except for the initial cohort, patients in all subsequent cohorts were enrolled concurrently.

Table JPBA.6.1. Dose-Escalation Scheme for Study I3Y-MC-JPBA

| Cohort | Patients/Cohort | LY2835219 Dose |
|--------|-----------------|----------------|
| 1 | 3 | 50 mg Q24H |
| 2 | 3 | 100 mg Q24H |
| 3 | 3 | 150 mg Q24H |
| 4 | 3 | 225 mg Q24H |
| 5 | 3 | 75 mg Q12H |
| 6 | 3 | 100 mg Q12H |
| 7 | 3 | 150 mg Q12H |
| 8 | 3 | 200 mg Q12H |
| 9 | 3 | 275 mg Q12H |
| 10 | 3 | 350 mg Q12H |
| 11 | 3 | 450 mg Q12H |

Abbreviations: Q24H = every 24 hours, Q12H = every 12 hours.

Note: Cohorts 1-4 received study drug Q24H on the once daily schedule.

The dose-escalation phase was guided by safety assessments from Days -3 through 29 of Cycle 1 for all patients in the cohort and also by the emerging PK data from previous cohorts. If none of the patients in a cohort experienced a DLT, dose escalation could occur to the next prespecified dose level. For all cohorts, if safety assessments and/or the emerging PK data indicated either that dose escalation should occur to a dose level lower than the next prespecified dose level or that dose de-escalation should occur to a dose level lower than the current dose level, then safety assessments and/or the emerging PK data could be used to select an alternate dose level within these constraints. Dose escalation occurred until the MTD (defined in Section 6.2.2.1) was established at 200 mg every 12 hours for the twice daily schedule.

Dose escalation, unless guided by the emerging PK data as described above, proceeded as indicated in Table JPBA.6.1 until 1 patient experienced a DLT; thereafter, all subsequent patients in that cohort were enrolled sequentially. If a DLT occurred in only 1 of 3 patients at a given dose level, up to 6 patients could be treated at that dose level; however, a total of 6 patients had to be treated at that dose level without further occurrences of a DLT before dose escalation could resume. If a DLT occurred in more than 1 patient at a given dose level, then the MTD had been exceeded and both dose escalation and enrollment to the cohort ceased. However, following discussion and agreement with investigators, additional patients could be treated at intermediate doses between the previous dose level and the dose level that exceeded the MTD to define the MTD more precisely.

In this study, intrapatient dose escalation was not permitted and dose escalation to the next cohort could not occur without prior discussion and agreement between the investigator and the responsible Lilly CRP.

6.2.2.1. Dose-Limiting Toxicity Determination and Maximum Tolerated Dose Definition

Dose-limiting toxicity (DLT) is defined as an AE occurring between Day -3 and Day 29 of Cycle 1 for a patient enrolled in Part A that is possibly related to the study drug and fulfills any one of the following criteria:

- Grade 3 or 4 nonhematological toxicity according to the NCI Common Terminology Criteria for Adverse Events (CTCAE CCI [REDACTED] except for nausea, vomiting, diarrhea, or electrolyte disturbance.
- Grade 3 or 4 nausea, vomiting, diarrhea, or electrolyte disturbance that persists more than 2 days despite maximal supportive intervention.
- Grade 4 hematological toxicity that persists more than 5 days.
- Grade 3 or 4 thrombocytopenia with bleeding.
- Grade 3 or 4 neutropenia with fever.

Investigators, together with the Lilly CRP, can declare a DLT if a patient is experiencing increasing toxicity during treatment, and it becomes clear that it is not going to be possible to complete the treatment without exposing the patient to excessive risk.

A DLT-equivalent toxicity is defined as an AE that would have met the criteria for DLT if it had occurred during Cycle 1 for a patient enrolled in Part A but that occurs between 1) Day 1 and Day 28 of Cycle 2 and beyond for a patient enrolled in Part A; 2) Day 1 and Day 29 of Cycle 1 for a patient enrolled in Parts B, C, D, E, F, or G; or 3) Day 1 and Day 28 of Cycle 2 and beyond for a patient enrolled in Parts B, C, D, E, F, or G.

Maximum tolerated dose (MTD) is defined as the highest dose level at which less than 33% of patients experience a DLT during Cycle 1.

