6.2.3. Dose Confirmation Phase (Parts B, C, D, E, F, and G)

After the MTD has been identified in Part A, at least 15 and up to 45-60 patients will be enrolled in each of the 6 tumor-specific expansions: Part B (non-small cell lung cancer), Part C

(glioblastoma multiforme), Part D (breast cancer), Part E (melanoma), Part F (colorectal cancer), and Part G (HR+ breast cancer).

During the dose confirmation phase, patients may enroll concurrently and will be treated at a dose no greater than the MTD (200 mg every 12 hours). Patients enrolled under JPBA amendment (f) who are still receiving LY2835219 at a dose of 150 mg every 12 hours may, at the discretion of the investigator, be escalated to 200 mg every 12 hours. Patients enrolled under JPBA amendment (g) or subsequent amendment should initially receive LY2835219 at a dose of 200 mg every 12 hours. For all patients, dose adjustments are permitted as outlined in Section 6.2.4.1.

If DLT-equivalent toxicities occur in 33% or more of patients within a tumor-specific cohort expansion, then investigators and the Lilly CRP will assess the nature and severity of these toxicities. No additional patients will be accrued until this safety review is completed and a decision is made either to continue at the current dose or to deescalate the dose and define a new dose for the expansion phase. The safety review and decision will be documented in writing.

During the dose confirmation phase, paired tumor biopsies should be obtained, whenever clinically feasible, before (Day -14 to Day -4) and after (Day 8 to Day 22) administration of study drug in Cycle 1.

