a Females with child bearing potential must have a negative serum pregnancy test within 3 days of the first dose of study drug (i.e., Day-6 to Day-4).

b Chest X-ray may be omitted in patients having a chest CT as part of their radiological tumor assessment. Radiological tumor assessment, including Chest X-ray, is performed at baseline (Day -28 to Day-4), then between Day 21 and Day 28 of every other cycle beginning with Cycle 2.

c Obtain only after study eligibility is confirmed.

[figure not shown]
d All drug- or procedure-related adverse events and serious adverse events should be followed until they resolve, are no longer considered to be drug- or procedure-related, become stable or return to baseline, the patient starts a new therapy, the patient dies, or the patient becomes lost to follow-up. Frequency of evaluation is left to the judgment of the investigator.

e A central ECGs (no replicates required) should be obtained at baseline (Day-14 to Day-4) and at the following time points during Cycle 1 only: pre-dose, 2 and 4 hrs post-dose on Day-3; both Day-2 and Day-1 (as close to PK sample collection as possible); predose, 2 and 4 hrs postdose on Day 15.

f For the once daily schedule, LY2835219 is to be administered every 24 hours on Days 1 through 28 of each cycle except in Cycle 1, when study drug will be administered as a single (morning) dose on Day -3 and then every 24 hours on Days 1 to 27. For the twice daily schedule, LY2835219 is to be administered every 12 hours on Days 1 through 28 of each cycle except in Cycle 1, when LY2835219 will be administered as a single (morning) dose on Day -3, every 12 hours on Days 1 to 27, and as a single (morning) dose on Day 28. Patients should not consume food beginning 1 hour before and ending 1 hour after taking study drug.

Study Schedule 1: Assessments for Parts A, B, C, D, E, F, and G (Concluded)

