**Table JPBA 6.1. Data Handling Conventions**

Term	Definition or Rule
Entered	Patients entered into the trial as those who sign the informed consent document directly or through their legally acceptable representatives.
Enrolled	Patients who are enrolled in the trial are those who have been assigned to a treatment.
On therapy	Patients who have received at least one dose of LY2835219.
Phase	This study has 2 phases: Dose Escalation Phase (Part A) and Dose Confirmation Phase (Part B, C, D, E F, and G).
Study day	
 
• There is no study day 0. Day -1 is the day before the day 1 of cycle 1 of each phase.
 
• Day -3 of cycle 1 of Dose Escalation Phase is the first dose of LY2835219.
 

Cycle day	
 
• There is no cycle day 0. Cycle day -1 is the day before the cycle day 1 of cycle 1 of each phase.
 
• Day -3 of cycle 1 is the first dose of LY2835219 in each phase. Day 1 of cycle 2 and beyond is the first dose of LY2835219 within cycle for each phase.
 

Treatment Day	Treatment Day relative to first day of the study (Cycle 1 Day -3).
Baseline	
For change from baseline analyses, baseline value is defined as the last reported measure on or before the first dose date (prior to the dose administration), unless otherwise specified.
 
For change from baseline within a cycle, baseline value is defined as the measure prior to the first dose of that cycle, unless otherwise specified.

The following are the General Reporting Requirements for the non-PK analyses (Table JPBA.6.2).

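### Parts B to G count DLT-equivalent toxicities from Day 1 although the first dose is on Day -3, so an event that qualifies and resolves on Days -3 to -1 is left out of the 33% accrual hold

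*Protocol*

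**What the plan says.** Protocol 6.2.2.1 sets the counting windows. A Part A DLT is "an AE occurring between Day -3 and Day 29 of Cycle 1 for a patient enrolled in Part A". The DLT-equivalent toxicity for the expansions uses the same criteria, but its Cycle 1 window lies between "Day 1 and Day 29 of Cycle 1 for a patient enrolled in Parts B, C, D, E, F, or G". For later cycles the window is Day 1 to Day 28.

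The expansions follow the twice daily schedule: in each, "at least 15 and up to 45-60 patients will be treated on the twice daily schedule" (Protocol 5.2). On that schedule "the initial dose of study drug will be taken on Day -3 to enable PK sampling over 72 hours following a single dose" (Protocol 6.2.1). Footnote f of Attachment 1, in the schedule headed for all Parts A to G, describes Cycle 1 in the same way: "when LY2835219 will be administered as a single (morning) dose on Day -3, every 12 hours on Days 1 to 27". The SAP agrees in Table JPBA 6.1: "Day -3 of cycle 1 is the first dose of LY2835219 in each phase".

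The count feeds the accrual hold in Protocol 6.2.3: "If DLT-equivalent toxicities occur in 33% or more of patients within a tumor-specific cohort expansion", the toxicities are reviewed and accrual pauses until a decision is made. The SAP repeats this rule in 6.1.1.

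For the expansions, SAP 6.1.1 treats similar events as equivalent toxicities in any cycle, and SAP 6.3.5.1 lists and summarizes them for every cycle other than Part A Cycle 1. Neither section gives day limits for the expansions.

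**The concern.** The toxicity window should open when exposure begins. In Part A it does. In Parts B to G it opens three days after the first dose, and no reason is given. The same related Grade 3 event, starting and resolving on Day -2, is a DLT in Part A and is not a DLT-equivalent toxicity in an expansion.

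The 33% rule is the only numerical accrual hold that can be read in the documents for the expansions. Protocol 5.2 calls the twice daily MTD tentative pending dose confirmation, so this count is part of how that dose is checked. A programmer who builds the DLT-equivalent flag from the Protocol would exclude Days -3 to -1. One who builds it from the SAP, which labels Day -3 as belonging to Cycle 1 and sets no day limits, would probably include them.

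**Working it through.** **Step 1. Confirm that a dose precedes the window.** Protocol 6.2.1 states 55 doses remaining in Cycle 1 after the Day -3 dose. Twice daily on Days 1 to 27 plus one dose on Day 28 gives 27 × 2 + 1 = 55. The figure reproduces, and with Day -3 the total is 56. Attachment 4 shows no dose on Days -2 and -1, so the gap holds one dose.

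**Step 2. Length of the gap.** SAP Table JPBA 6.1 states that there is no Day 0.

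- Part A: 3 days (Days -3 to -1) + 29 days = 32 days.
- Parts B to G: 29 days.
- Difference: 3 days; 3/32 = 9.4%.

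**Step 3. Which events are lost.** This depends on the criteria in Protocol 6.2.2.1, which are the same for all parts.

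- Grade 3 or 4 nonhematological toxicity in general, thrombocytopenia with bleeding, and neutropenia with fever carry no minimum duration. Such an event can qualify and resolve before Day 1, and is then not counted.
- Nausea, vomiting, diarrhea and electrolyte disturbance must last more than 2 days. Onset on Day -3 could qualify by Day -1. Onset on Day -2 or -1 can qualify only by lasting into Day 1 or later.
- Grade 4 hematological toxicity must last more than 5 days. Onset on Day -3 qualifies at about Day 3, inside the window.
- For an event that straddles Day 1, the text says only that it *occurs* in the window. It does not say whether onset or presence decides, so the event may or may not count.

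**Step 4. Effect on the hold.** The smallest k with k/n ≥ 0.33, and the result with one patient fewer:

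| n | k for a hold | k/n | (k − 1)/n |
|---|---|---|---|
| 15 | 5 | 33.3% | 26.7% |
| 45 | 15 | 33.3% | 31.1% |
| 60 | 20 | 33.3% | 31.7% |

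**Step 5. Illustration only.** Let f be the share of affected patients whose only qualifying event lies in the gap. The documents do not give f. Assume a true rate of 40% and one look at the full cohort; neither is in the documents. P(hold) is the binomial probability of at least k counted patients out of n, each counted with probability 0.40 × (1 − f).

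| f | n = 15 | n = 45 | n = 60 |
|---|---|---|---|
| 0 (gap closed) | 0.78 | 0.86 | 0.88 |
| 5% | 0.73 | 0.79 | 0.81 |
| 10% | 0.68 | 0.70 | 0.71 |
| 20% | 0.55 | 0.48 | 0.46 |

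With one dose in the gap, f may well be near zero.

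**Step 6. Later cycles (secondary).** Windows end at Day 28. Protocol 6.2.1 allows the next cycle to start up to 7 days late for other reasons and up to 14 days late for toxicity, and footnote p of Attachment 1 keeps Day 28 procedures done on Day 29 or 30 in the current cycle. A new event on those days falls in no window.

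**The case against.** The strongest reply is that little is lost. The gap holds 1 of 56 Cycle 1 doses (1.8%). The expansion count runs over all cycles, so with the two planned cycles the excluded share is 3/(3 + 29 + 28) = 3/60 = 5%. All adverse events from the first dose are reported (Protocol 7.1.2.2.2) and safety is reviewed continuously (9.3). Crossing 33% triggers a review that may end with no change. Protocol 4.7 shows the expansion starting dose being changed on the frequency of diarrhea and on clinical activity, without reference to this count. All of this stands. It limits the consequence but does not remove the gap from the formal rule.

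Four stronger readings are tempting, and the documents do not support them:

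- *Every event that starts on Days -3 to -1 is lost.* Only events that qualify and resolve before Day 1 clearly are (step 3).
- *The SAP states a contrary expansion window.* It states none. The fault is that the two documents do not settle on one window.
- *Up to 14 days of observation are lost with each delayed cycle.* The hold counts patients, and a patient delayed for a qualifying toxicity may already be counted. What falls out is a new event in a patient not yet counted.
- *Opening the window on Day -3 makes expansion rates comparable with the Part A rate.* It does not, because Part A counts Cycle 1 only and the expansions count all cycles.

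**Conclusion.** Wrong as written. The Part A and expansion windows stand in one section and open on different days, while the first dose falls on the same day; no other section closes the gap. The certain effect is that related events which qualify and resolve within three days of the single first dose are not counted in the hold. The uncertain effect is on events that last into Day 1.

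The size cannot be estimated from the documents. The thresholds in step 4 show only that one patient can decide the result, and the probabilities in step 5 rest on assumed values of f and of the true rate. This is not evidence that a safety signal went unseen. If expansion accrual has ended, the hold is moot, but the DLT-equivalent summaries in SAP 6.3.5.1 still need one definition.

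**What to change.** Reconcile Protocol 6.2.2.1 with Protocol 6.2.1, footnote f of Attachment 1, SAP 6.1.1 and SAP Table JPBA 6.1, and state one expansion counting window identically in Protocol 6.2.2.1 and SAP 6.1.1. The window should:

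- open at the first dose of study drug, as in Part A;
- leave no uncounted days between cycles;
- say whether onset or presence places an event in it.

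In the same edit, align the end of the Part A window, which is Day 29 in the Protocol and Day 28 in the SAP.

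The cost is about one line in each document, with no new data collection. The change affects which events are counted, not any dose or patient management. Its downside is that the hold may trigger slightly more often.
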